5.3.1 Adverse Event Reporting Period

Investigators will seek information on adverse events at each patient contact. All adverse events, whether reported by the patient or noted by study personnel, will be recorded in the patient's medical record and on the Adverse Event eCRF.

After informed consent has been obtained but prior to initiation of study treatment, only serious adverse events caused by a protocol-mandated intervention (e.g., invasive procedures such as biopsies, discontinuation of medications) should be reported (see Section 5.4.2 for instructions for reporting serious adverse events).

After initiation of study treatment, all adverse events will be reported until [REDACTED] days after the final dose of study treatment or [REDACTED], and serious adverse events will continue to be reported until [REDACTED] days after the final dose of study treatment [REDACTED].

[REDACTED]. In addition, adverse events of special interest will continue to be reported until [REDACTED] days after the final dose of study treatment, [REDACTED].

Instructions for reporting adverse events that occur after the adverse event reporting period are provided in Section 5.6.

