5.4.2.2 Events That Occur after Study Treatment Initiation

After initiation of study treatment, serious adverse events will be reported until 90 days after the final dose of study treatment or until initiation of new systemic anti-cancer therapy, whichever occurs first. In addition, adverse events of special interest will continue to be reported until 90 days after the final dose of study treatment, regardless of initiation of new anti-cancer therapy. Investigators should record all case details that can be gathered immediately (i.e., within 24 hours after learning of the event) on the

Adverse Event eCRF and submit the report via the electronic data capture (EDC) system. A report will be generated and sent to Roche Safety Risk Management by the EDC system.

In the event that the EDC system is unavailable, the paper Clinical Trial Adverse Event/Special Situations Form provided to investigators should be completed and submitted to the Sponsor or its designee immediately (i.e., no more than 24 hours after learning of the event), either by faxing or by scanning and emailing the form using the fax number or email address provided to investigators. Once the EDC system is available, all information will need to be entered and submitted via the EDC system.

Instructions for reporting serious adverse events that occur after the reporting period are provided in Section 5.6.

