5.6 ADVERSE EVENTS THAT OCCUR AFTER THE ADVERSE EVENT REPORTING PERIOD

After the end of the reporting period for serious adverse events and adverse events of special interest (as defined in Section 5.3.1), all deaths, regardless of cause, should be reported through use of the Long-Term Survival Follow-Up eCRF.

In addition, if the investigator becomes aware of a serious adverse event that is believed to be related to prior exposure to study treatment, the event should be reported through use of the Adverse Event eCRF. However, if the EDC system is not available, the investigator should report these events directly to the Sponsor or its designee, either by faxing or by scanning and emailing the paper Clinical Trial Adverse Event/Special Situations Form using the fax number or email address provided to investigators.

5.7 EXPEDITED REPORTING TO HEALTH AUTHORITIES, INVESTIGATORS, INSTITUTIONAL REVIEW BOARDS, AND ETHICS COMMITTEES

The Sponsor will promptly evaluate all serious adverse events and adverse events of special interest against cumulative product experience to identify and expeditiously communicate possible new safety findings to investigators, IRBs, ECs, and applicable health authorities based on applicable legislation.

The Sponsor has a legal responsibility to notify regulatory authorities about the safety of a study treatment under clinical investigation. The Sponsor will comply with regulatory requirements for expedited safety reporting to the regulatory authorities (which includes the use of applicable systems, such as EudraVigilance), IRBs, ECs, and investigators.

To determine reporting requirements for single adverse event cases, the Sponsor will assess the expectedness of these events through use of the reference safety information in the documents listed below:

| Drug | Document |
|--------------|---|
| Tiragolumab | Tiragolumab Investigator's Brochure |
| Atezolizumab | Atezolizumab Investigator's Brochure |
| Durvalumab | E.U. Summary of Product Characteristics |

The Sponsor will compare the severity of each event and the cumulative event frequency reported for the study with the severity and frequency reported in the applicable reference document.

Reporting requirements will also be based on the investigator's assessment of causality and seriousness, with allowance for upgrading by the Sponsor as needed.

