##### **4.5.2 Adverse Events**

Verbatim description of AEs will be mapped to the Medical Dictionary for Regulatory Activities (MedDRA) thesaurus terms. Severity for all treatment-emergent AEs will be graded by the investigator according to National Cancer Institute Common Terminology Criteria for Adverse Events (NCI CTCAE) v5.0, and severity for cytokine release

syndrome (CRS) will also be graded by the investigator according to the American Society for Transplantation and Cellular Therapy (ASTCT) consensus grading scale.

All AEs will be summarized by treatment arm and NCI CTCAE grade. Cytokine-release syndrome will also be summarized by treatment arm and ASTCT consensus grade. In addition, common AEs, treatment-related AEs, serious adverse events (SAEs), AEs leading to study treatment discontinuation or interruption, Grade 3-4 AEs, and fatal AEs (Grade 5) will be summarized accordingly. For the purpose of analyses, adverse event of special interest (AESI) are identified by a set of comprehensive definitions using standardized MedDRA queries (SMQs), High-Level Terms (HLT), Preferred Terms (PTs) and Sponsor-defined custom events (CEs) from the AE clinical database by medical concept. Multiple occurrences of the same event will be counted once at the maximum severity.

For the safety analyses, “treatment-emergent” is defined as AEs occurring on or after the first dose of study drug treatment or as a pre-existing condition that worsened on or after the first dose of the study treatment up to the data cutoff date.

Listings of AEs will include all treatment emergent AEs up to the data cutoff date.

All deaths and causes of death will be summarized by treatment arm.

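### SAP 4.5.2 counts adverse events as treatment-emergent up to data cutoff, but after the protocol's reporting window only serious and special-interest events judged related are collected, so the safety tables mix two kinds of event

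*SAP*

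**What the plan says.** **Analysis window (SAP 4.5.2).** An event is treatment-emergent if it starts on or after the first dose, or if it is a pre-existing condition that "worsened on or after the first dose of the study treatment up to the data cutoff date". The listings have the same end point: "Listings of AEs will include all treatment emergent AEs up to the data cutoff date". The tables are broad: "All AEs will be summarized by treatment arm and NCI CTCAE grade". Serious, Grade 3-4, fatal (Grade 5), treatment-related and special-interest events get their own summaries.

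**Collection window (protocol 5.3.1 and 5.4.2.2).** Collection after the last dose is time-limited.
- For events in general: "After initiation of study treatment, all adverse events will be reported until" a fixed number of days after the last dose. The number is redacted in the public text.
- For serious events: "serious adverse events will be reported until 90 days after the final dose of study treatment or until initiation of new systemic anti-cancer therapy", whichever comes first.
- For special-interest events: "adverse events of special interest will continue to be reported until 90 days after the final dose of study treatment", and new anti-cancer therapy does not close this window.

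**After the window (protocol 5.6 and 3.1.1).** Section 5.6 asks for a further report "if the investigator becomes aware of a serious adverse event that is believed to be related to prior exposure to study treatment". In that case "the event should be reported through use of the Adverse Event eCRF", the form also used inside the window. Section 3.1.1 adds related special-interest events. Under 5.6, deaths from any cause continue to be reported, on a separate long-term survival form.

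**The concern.** An incidence table assumes one ascertainment rule for everything it counts. Here the rule changes part-way through the period that the SAP calls treatment-emergent. Up to the end of the window an event is recorded whatever its cause. After it, a serious or special-interest event is recorded only if it comes to the investigator's notice and the investigator believes study treatment caused it. That belief is formed in an open-label trial.

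The all-cause window for serious events also closes when new systemic anti-cancer therapy starts, whereas the SAP's definition stays open. If the arms differ in when patients start new therapy, the change of rule comes at different times by arm.

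What is at stake is how the between-arm serious, Grade 3-4, Grade 5 and special-interest percentages are read. They could reflect attribution and length of follow-up as well as toxicity.

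**Working it through.** The plan states no figure for this point, so there is nothing to reproduce. The check compares the collection rules with the analysis rule.

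| Event class | Collected for any cause until | Collected afterwards | SAP 4.5.2 counts until |
|---|---|---|---|
| Serious | 90 days after last dose, or new systemic therapy if earlier | Only if believed related (5.6, 3.1.1) | Data cutoff |
| Special interest | 90 days after last dose | Only if believed related (3.1.1) | Data cutoff |
| Other adverse events | Fixed period after last dose (days redacted) | Not collected | Data cutoff, but no data |
| Deaths, all-deaths summary | Throughout | Any cause, separate form (5.6) | No mixing |

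The first two rows are where the mismatch lies. Late related serious events go on the ordinary adverse event form, so under the SAP's definition they enter the same tables as in-window events. Neither the readable SAP text nor protocol 6.6 limits those tables to the reporting period. A late fatal event would reach the Grade 5 adverse event table only if it was reported as related.

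**When all-cause collection ends.** The inputs are 13 cycles of 28 days (SAP Table 1) and 90 days after the last dose (protocol 5.4.2.2), for a patient who takes every dose without delay.
- Dosing every 4 weeks: last dose on day 12 × 28 + 1 = 337. The window ends on day 337 + 90 = 427, or 427 / 30.4375 = 14.0 months.
- Durvalumab every 2 weeks: last dose on day 12 × 28 + 15 = 351. The window ends on day 351 + 90 = 441, or 441 / 30.4375 = 14.5 months.

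Delayed doses move these days later. Stopping early moves them earlier, as does new systemic therapy for serious events.

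**Share of follow-up under the related-only rule.** The formula is 1 − (window end) / (365.25 × years). The readable text gives no cutoff date, so the 2-, 3- and 4-year follow-up times are assumptions. Eight years is the approximate maximum participation in protocol 3.3 and is not the cutoff of any named analysis.

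| Follow-up | Window ends day 427 | Window ends day 441 |
|---|---|---|
| 2 years | 41.5% | 39.6% |
| 3 years | 61.0% | 59.8% |
| 4 years | 70.8% | 69.8% |
| 8 years | 85.4% | 84.9% |

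These are shares of time, not of events.

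**What one late event does.** With about 800 / 2 = 400 patients per arm, one patient whose only serious event is a late related one moves that arm's serious-event percentage by 1 / 400 = 0.25 percentage points. The between-arm shift is the difference between the arms in such patients. The documents give no basis for a number in either arm, and equal rates give a shift of zero.

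**The case against.** The strongest reply is that the practical effect may be negligible, and that counting every recorded post-dose event keeps late immune-mediated toxicity in the main table. Several parts of this stand.
- Other late events are not collected, so most of the all-events table is bounded by collection whatever the SAP says.
- The summary of all deaths is sound, because deaths of any cause are still reported.
- The adverse event outputs are descriptive, with no hypothesis test, and treatment-related events have their own summary.
- Late events may be few.

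A reader might infer more: that investigators will attribute late events more readily to the new combination, so the tables are biased against it. The documents do not support that direction. Protocol 5.3.4 applies one causality rule to both arms, with related as the default. Protocol 5.1.4 gives the comparator a long list of immune-mediated risks, so late related reports are plausible in either arm. Protocol 5.1.1 does say that not all tiragolumab risks are known, and 5.1.5.2 tells investigators to attribute immune-mediated events generally to both experimental drugs. The second instruction mainly concerns attribution between those two drugs. Neither passage establishes a difference between arms.

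None of this removes the inconsistency. It limits what can be claimed about its effect.

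**Conclusion.** The mismatch holds on readable text and is not a product of redaction. As written, the serious, Grade 3-4, Grade 5 and special-interest summaries put all-cause events from inside the reporting window together with related-only events from after it. Because the serious-event window closes at new systemic therapy, the change of rule can occur at different times by arm.

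The size and direction of any bias cannot be stated from the documents. For a fully treated patient with no delays, the related-only period begins after day 427 or 441, depending on the dosing schedule. A later cutoff lengthens that period without lengthening the all-cause one. The conclusion assumes that no redacted SAP text restricts these tables, and none of the readable text does. This is a cheap improvement of low severity and does not undermine the safety analysis as a whole.

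**What to change.** In SAP 4.5.2, end the treatment-emergent window for the main adverse event tables at the protocol's reporting period for each event class, by reference to protocol 5.3.1 and 5.4.2.2. The reference also covers events that are neither serious nor of special interest, whose day count is redacted here.

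State that an event meeting more than one class uses the longer window. A serious special-interest event that starts after new therapy but within 90 days of the last dose would then stay in the main tables. Class should mean the protocol's reporting class, since the SAP builds its special-interest tables from MedDRA groupings that need not coincide with it.

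Tabulate later related serious and special-interest events separately by arm. Including the special-interest events matters, because late non-serious ones would otherwise appear in neither table.

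Reconcile protocol 3.1.1 with 5.6. As worded, 3.1.1 can be read as limiting late death reports to related ones, and it includes special-interest events. Section 5.6 takes all deaths and names only serious events.

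The SAP change costs one sentence and one table, and no data are lost. The small downside is that late immune-mediated events move from the main table to the separate one.

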#### **4.5.3            Additional Safety Assessments**

##### **4.5.3.1        Laboratory Data**

Laboratory data will be graded according to NCI CTCAE v5.0 and will be summarized descriptively by treatment arm. Shift tables from baseline to worst post-baseline value will also be presented.

##### **4.5.3.2        Vital Signs**

Vital signs outside normal limits among patients without abnormality at baseline will be summarized by treatment arm.

#### **4.6              OTHER ANALYSES**

##### **4.6.1           Summaries of Conduct of Study**

Study enrollment and reasons for discontinuation from the study will be summarized by treatment arm in the PPAS and FAS. Major protocol deviations, including major deviations with regards to the inclusion and exclusion criteria, will be summarized by treatment arm for the FAS. Study treatment disposition and reasons for study drug discontinuation will be summarized by treatment arm in the SAS.

##### **4.6.2           Summaries of Treatment Group Comparability**

Demographics (including age, sex, race) and baseline characteristics (e.g., PD-L1 expression, previous curative treatment, and ECOG Performance Status) will be

summarized overall and by treatment arm for both PPAS and FAS. Descriptive statistics (mean, median, standard deviation, and range) will be presented for continuous data, and frequencies and percentages will be presented for categorical data, as appropriate.

#### **4.6.3      Pharmacokinetic Analyses**

Samples will be collected for pharmacokinetic (PK) analyses and to compare exposure in this study with that attained in previous studies. PK analyses will be conducted as appropriate based on the availability of data.

Serum concentrations of tiragolumab and atezolizumab will be reported as individual values and summarized (mean, standard deviation, coefficient of variation, median, range, geometric mean, and geometric mean coefficient of variation) by treatment arm and cycle, when appropriate and as data allow. Individual and median serum tiragolumab and atezolizumab concentrations will be plotted by treatment arm and day. Tiragolumab and atezolizumab concentration data may be pooled with data from other studies using an established population-PK model to derive PK parameters such as clearance, volume of distribution, and area under curve (AUC), as warranted by the data. Potential correlations of relevant PK parameters with safety, efficacy, or biomarker outcomes may be explored.

#### **4.6.4      Immunogenicity Analyses**

The immunogenicity analyses will include patients with any tiragolumab and/or atezolizumab anti-drug antibody (ADA) assessments, with patients grouped according to treatment received.

The number and proportion of treatment-emergent ADA-positive patients and ADA-negative patients during both the treatment and follow-up periods for both tiragolumab and atezolizumab will be summarized by treatment arm.

[REDACTED]

[REDACTED]

[REDACTED]

[REDACTED]

[REDACTED]

[REDACTED]

[REDACTED]

[REDACTED]

[REDACTED]

## **5. SUPPORTING DOCUMENTATION**

This section is not applicable, since there is no additional supporting document.

